4.2 RATIONALE FOR STUDY DESIGN

This study will assess the relative bioavailability of newly developed formulations of GDC-0134 compared to the current clinical material in healthy females of non-childbearing potential. A single dose, randomized, 2 part, 2-period crossover study design was considered acceptable to achieve the study objectives. This study will not be blinded as the primary endpoints (GDC-0134 PK) are not subjective or able to be biased by knowledge of study sequence.

4.3 RATIONALE FOR SUBJECT POPULATION

The study will exclude women of childbearing potential and will be limited to healthy female subjects of non-childbearing potential based on findings of maternal toxicity and significant fetal malformations in nonclinical studies in pregnant rats and rabbits (see Section 2.1 and the IB [10] for further details). Males are excluded based on findings of testicular toxicity observed in male rats (see Sections 6.1.4.10). Clinical experience in humans is still limited to assess the translatability of these nonclinical findings to humans.

4.4 RATIONALE FOR EXPLORATORY ASSESSMENTS

Urine samples will be collected to determine urinary elimination of GDC-0134.

4.5 RATIONALE FOR PHARMACOKINETIC SAMPLING SCHEDULE

The frequent sampling schedule is designed to capture data at a sufficient number of timepoints to provide a detailed profile of the concentration-time curve, including maximum observed concentration (C_{max}), time to maximum observed concentration (t_{max}), and apparent terminal elimination half-life ($t_{1/2}$).

4.6 RATIONALE FOR WHOLE GENOME SEQUENCING

A whole blood sample will be collected from all subjects for DNA extraction to enable whole genome sequencing (WGS). Genomics is increasingly informing researcher's understanding of disease pathobiology. Whole genome sequencing provides a comprehensive characterization of the genome and, through the generation of control data from healthy subjects along with clinical data collected in this study, may increase our understanding of PK, response, human diseases, and the opportunity for developing new therapeutic approaches. Data will be analyzed in the context of this study but will also be explored in aggregate with data from other studies. The availability of a larger dataset will assist in identification of important pathways, guiding the development of new targeted agents. Given the complexity and exploratory nature of these analyses, WGS data and analyses will not be shared with the Principal Investigators (PIs) or study subjects unless required by law.

5 SUBJECT SELECTION

Twenty-two healthy volunteer female subjects of non-childbearing potential who meet all the protocol inclusion criteria and none of the exclusion criteria will be enrolled into each part of the study. If the two parts of the study are run sequentially, subjects will be encouraged to participate in multiple parts of the study as long as they continue to meet the eligibility criteria. If the parts are conducted sequentially, any subjects discontinued may be replaced with new subjects prior to the start of each part. The maximum possible number of subjects enrolled into the study will be approximately 44.

5.1 SCREENING PROCEDURES

Refer to Table 7-1 and Table 7-2 for procedures performed for all potential subjects at the Screening visit.

If subjects are participating in multiple parts of the study, they will not be required to re-screen for the second part of the study as long as there are ≤ 28 days between Clinic Discharge in the first part and Check-in for the second part of the study.

5.2 CHECK-IN PROCEDURES

Refer to Table 7-1 and Table 7-2 for procedures performed at Check-in for Periods 1 and 2 when subjects will report to the study site.

For subjects to continue their participation in the study, the drug screen and pregnancy test must be negative and the clinical laboratory evaluations must be within the normal laboratory range (unless deemed not clinically significant by the PIs). In addition, continued compliance with concomitant medication and other restrictions will be verified.

5.3 INCLUSION CRITERIA

Subjects who meet the following criteria may be included in the study:

- Females, between 18 and 65 years of age, inclusive; within body mass index (BMI) range 18.5 to 35 kg/m², inclusive;
- 2. In good health, determined by no clinically significant findings from medical history, physical examination, 12-lead ECG, and vital signs;
- 3. Clinical laboratory evaluations (including chemistry panel [fasted at least 8 hours], complete blood count [CBC], and urinalysis [UA] with complete microscopic analysis (if indicated) within the reference range for the test laboratory, unless deemed not clinically significant by the PIs [Gilberts syndrome is acceptable]);
- 4. A normal ophthalmology assessment; minor abnormalities or age-related changes are acceptable, if not considered clinically significant, as per the judgment of the ophthalmologist;
- 5. Negative test for selected drugs of abuse at Screening (does not include alcohol) and at Check-in for each study period (does include alcohol; Appendix A);
- 6. Negative for cannabinoids (tetrahydrocannabinol) at Screening and at Check-in for both study periods (Appendix A);
- 7. Negative hepatitis panel (hepatitis B virus core antibody, hepatitis B surface antigen [HBsAg] and hepatitis C virus antibody [anti-HCV]) and negative HIV antibody screens (Appendix A);
- 8. Females of non-childbearing potential only, defined as:
 - females who are permanently sterile via hysterectomy, bilateral salpingectomy, and/or bilateral oophorectomy by reported medical history and/or medical records. Surgical sterilization to have occurred a minimum of 6 weeks prior to Screening
 - Females of at least 45 years of age with amenorrhea for 12 months without an alternative medical reason with confirmatory follicle-stimulating hormone (FSH) levels of ≥40 mIU/mL. The amenorrhea should not be induced by a medical condition such as anorexia nervosa, hypothyroid disease or polycystic ovarian disease, or by extreme exercise. It should not be due to concomitant medications that may have induced the amenorrhea such as oral contraceptives, hormones, gonadotropin-releasing hormones, anti-estrogens, or selective estrogen receptor modulators. Women aged > 60 years old whose

FSH values are not \geq 40 mIU/L may be included at the discretion of the PIs and in consultation with the Sponsor

- 9. Negative screening test for latent mycobacterium tuberculosis (TB) infection by QuantiFERON® TB Gold (Appendix A). Indeterminate results may be confirmed By repeat or by a purified protein derivative (PPD) skin test;
- 10. Receive an explanation of the mandatory WGS component of the study;
- 11. Able to comprehend and willing to sign an Informed Consent Form (ICF).

5.4 EXCLUSION CRITERIA

The following will exclude potential subjects from the study:

- Significant history or clinical manifestation of any metabolic, allergic, dermatological, hepatic, renal, hematological, pulmonary, cardiovascular (including left ventricular hypertension), gastrointestinal (GI), neurological, ophthalmologic, or psychiatric disorder, as determined by the PI (or designee);
- 2. History of significant hypersensitivity, intolerance, or allergy to any drug compound, food, or other substance, unless approved by the PI (or designee);
- 3. History of stomach or intestinal surgery or resection (including cholecystectomy) that would potentially alter absorption and/or excretion of orally administered drugs except that appendectomy and hernia repair will be allowed;
- 4. History or presence of an abnormal ECG at Screening or Check-in (Day -1) for Period 1, which in the PIs opinion, is clinically significant (QTc interval >470 msec, PR interval >210 msec, or QRS complex >120 msec; abnormal ECG findings will be confirmed by calculating the mean of the original value and 2 repeats);
- 5. History of alcoholism or drug addiction within 1 year prior to Check-in (Day -1) for their first treatment period;
- 6. Participation in any other investigational study drug trial in which receipt of an investigational study drug occurred within five half-lives (if known) or 30 days (small molecule) or 90 days (biologic) for Check-in (Day -1) of their first treatment period, whichever is longer;
- 7. Use of any prescription medications/products within 14 days prior to Check-in (Day -1) for their first treatment period and during the entire study duration, unless deemed acceptable by the PI (use of hormone replacement therapy [HRT], thyroid replacement therapy, ophthalmic drops, or other ophthalmic procedures as part of the fundoscopic exam is acceptable);
- 8. Use of oral antibiotics within 4 weeks or intravenous antibiotics within 8 weeks prior to the Screening evaluation and during the entire study duration;

- 9. Use of any over-the-counter, non-prescription preparations (including vitamins; minerals; and phytotherapeutic-, herbal-, and plant-derived preparations) within 14 days prior to Check-in (Day -1) for their first treatment period and during the entire study duration, unless deemed acceptable by the PI (acetaminophen [paracetamol] is acceptable [see Section 7.5]);
- Use of acid reducing medications (PPIs, H2 receptor antagonists, etc.) within 14 days prior to Check-in (Day -1) for their first treatment period and during the entire study duration. As an alternative, antacids may be allowed at least 4 hours before or after dose;
- Use of strong inhibitors and inducers of CYP3A4/5 and UGT enzymes within 14 days prior to Check-in (Day -1) for their first treatment period until the Study Completion/ET is prohibited, and alternate medications should be considered where possible;
- 12. Use of any vaccines (including seasonal flu and H1N1 vaccines) within 14 days prior to Check-in (Day -1) for their first treatment period;
- 13. Use of tobacco- or nicotine-containing products (including, but not limited to, cigarettes, e-cigarettes, pipes, cigars, chewing tobacco, nicotine patches, nicotine lozenges, or nicotine gum) within 6 months prior to Check-in (Day -1) for their first treatment period and during the entire study;
- 14. Use of alcohol- or caffeine-containing foods or beverages within 72 hours prior to Check-in (Day -1) for their first treatment period until Study Completion/ET;
- 15. Consumption of grapefruit, grapefruit-containing products, and pomegranate, pomelo, and star fruit juice/products within 7 days prior to Check-in (Day -1) for their first treatment period and during the entire study duration;
- 16. strenuous exercise within 48 hours prior to Check-in (Day -1) for their first treatment period or during the period of confinement at the study site (e.g., subjects will not begin a new exercise program or participate in any unusually strenuous physical exertion);
- 17. Poor peripheral venous access;
- 18. History of malignancy, except for appropriately treated carcinoma in situ of the cervix, non-melanoma skin carcinoma, or Stage I uterine cancer;
- 19. Donation of blood from 30 days prior to Screening through Study Completion, Clinic Discharge, or ET, inclusive, or of plasma from 2 weeks prior to Screening through Study Completion, Clinic Discharge, or ET, inclusive;
- 20. Receipt of blood products within 2 months prior to Check-in (Day -1) for their first treatment period;

- 21. Subjects with best-corrected visual acuity worse than 20/40 in either eye, history of optic neuropathy, history of optic disc swelling or atrophy, and/or history of chronic eye disease (e.g., glaucoma, uveitis, diabetic retinopathy);
- 22. Any acute or chronic condition or any other reason that, in the opinion of the PI, would limit the subject's ability to complete and/or participate in this clinical study;
- 23. Any condition that would preclude participants from receiving a lumbar puncture during the study.

Subjects participating in multiple parts of the study:

- 24. Subjects that have received GDC-0134 within <28 days prior to Day 1
- 25. Subjects that have an ongoing AE which, in the opinion of the PI, prohibits them from further participation in the study

5.5 REMOVAL OF SUBJECTS FROM STUDY PARTICIPATION

Subjects will be informed that they are free to withdraw from the study at any time and for any reason. The PI may remove a subject from the study if, in the PIs opinion, it is not in the best interest of the subject to continue the study. Subjects may be discontinued due to the following: change in compliance with inclusion/exclusion criterion that is clinically relevant and affects subject safety, occurrence of AEs, occurrence of pregnancy, intake of non-permitted concomitant medication that might affect subject safety or study assessments/objectives, etc. Notification of discontinuation will immediately be made to the Sponsor's Study Monitor. In case of premature discontinuation of study participation, efforts will be made to perform all final study day assessments (see Section 7.16). The date the subject's electronic Case Report Form (eCRF). All dropouts will be followed until resolution of all their AEs or until the unresolved AEs are judged by the PI to have stabilized or returned to baseline.

For subjects who are discontinued by the PI or who voluntarily withdraw prematurely from the study, replacement subjects may be enrolled only if deemed necessary by the Sponsor. Except for replacements, the subjects will be assigned a number by study site staff. Assignment of numbers will be in ascending order and no numbers will be omitted. Subject numbers will be used on all study documentation. Replacement subjects will be assigned a subject number by adding 100 or 1000 to the number of the subject they are replacing (e.g., Subject No. 105 replaces Subject No. 005).

The entire study may be discontinued at the discretion of the PI, Sponsor, or Sponsor's Medical Monitor based on the occurrence of, but not limited to, the following:

- AEs unknown to date with respect to their nature, severity, and duration;
- Increased frequency, and/or severity, and/or duration of known AEs;
- Medical or ethical reasons affecting the continued performance of the study;
- Difficulties in the recruitment of subjects;*
- Cancellation of drug development.*

* For reasons that are not related to subject safety, the PI will discuss discontinuation of the entire study with the Sponsor prior to making any decisions.

6 ASSESSMENT OF SAFETY

6.1 SAFETY PLAN

GDC-0134 is not approved, and clinical development is ongoing. The safety plan for subjects in this study is based on clinical experience with GDC-0134 in completed and ongoing studies. The anticipated important safety risks for GDC-0134 are outlined below. Please refer to the IB (10) for more details on nonclinical studies in rats and cynomolgus monkeys, and preliminary clinical data

Several measures will be taken to ensure the safety of subjects participating in this study. Eligibility criteria have been designed to exclude subjects at higher risk for toxicities. Subjects will undergo safety monitoring during the study, including assessment of the nature, frequency, and severity of AEs.

6.1.1 RISKS ASSOCIATED WITH GDC-0134

There are no identified risks for GDC-0134.

6.1.2 CONTRAINDICATIONS WITH GDC-0134

There are no known contraindications for GDC-0134.

6.1.3 SERIOUS ADVERSE DRUG REACTIONS

No serious adverse drug reactions have been identified for GDC-0134.

6.1.4 POTENTIAL RISKS

6.1.4.1 Phototoxicity

A 3-day, multiple-dose phototoxicity study in rats showed no direct dermal effects, but ocular findings were observed in UVR-exposed rats and included inflammation and edema in the cornea and hyperplasia of the anterior lens epithelium. These findings were considered consistent with phototoxicity.

To prevent potential phototoxicity, subjects will be advised to avoid exposure to direct sunlight with the use of protective clothing, hats, sunglasses, and repeated application of sunscreen for 19 days after last dosing.

6.1.4.2 Skin Lesions

Skin lesions (erosions/ulcerations/scabs/sores/red discharge/alopecia) were observed in rats and monkeys with a dose-related effect. The tail was the most commonly affected area in monkeys, requiring amputation of the tail tip in some animals. Therefore, complete physical examinations, including a complete examination of the skin, will be conducted throughout the study to monitor for skin ulcerations or discolorations that may be indicative of study drug-induced toxicity. Limited, symptom-directed physical examinations may also be performed. In addition, subjects will be asked to do self-examinations on a daily basis.

6.1.4.3 Hypothermia

In repeat-dose toxicity studies in rats, mild reversible body temperature decreases of approximately 0.5°C were observed. In single- and repeat-dose toxicity studies of GDC-0134 in monkeys, dose-dependent decrease in oral body temperature was noted at higher doses in the 4-week study, but was not observed in the 39-week study. Body temperature will be monitored at baseline and during the study.

6.1.4.4 Retinal Toxicity

Nonclinical toxicology studies with DLK inhibitors have identified reversible peripapillary swelling (PPS) or optic disc edema by ocular examination and retinal nerve fiber layer (RNFL) thickening by optical coherence tomography in cynomolgus monkeys after multiple days of dosing that returns to near baseline after continued drug exposure in the majority of animals. However, in two instances a moderate decrease in RNFL thickness was observed after the transient thickening, and in one instance a continued RNFL thinning was observed 8 weeks after the end of drug exposure. The RNFL thickening was largely correlated with increased axon size.

In the two animals with thinning RNFL, increases in axon size were also noted by transmission electron microscopy (TEM) with one animal also observed to have minimally increased glial cell processes. There was no evidence of axonal loss or degeneration by TEM. On ophthalmic exams, no optic nerve head cupping was observed that would suggest elevated IOP as a factor for the RNFL thinning, and no GDC-0134-related effects were noted on IOP measurements, nor were any visual deficits detected in an animal, as assessed by electroretinography (full field and multi-focal ERGs) or visual evoked cortical potentials. No GDC-0134-related ophthalmic abnormalities, IOP effects, fundus photographic observations, or effects on rod- and cone-driven retinal function, as assessed by scotopic and photopic ERGs, have been observed. The functional consequences of this retinal change are unknown. Patients with best-corrected visual acuity worse than 20/40 in either eye, history of optic neuropathy, history of optic disc swelling or atrophy, and/or history of chronic eye disease (e.g. glaucoma, uveitis, diabetic retinopathy) are excluded from the GDC-0134 studies. Potential ocular toxicities will be evaluated at baseline and throughout GDC-0134 studies as shown in the Schedule of Activities (Table 7-1 and Table 7-2).

6.1.4.5 Increased Intracranial Pressure

As stated above, 4-week and 39-week nonclinical toxicology studies have identified reversible bilateral PPS or optic disc edema in cynomolgus monkeys. One potential mechanism of PPS or optic disc edema is increased intracranial pressure.

Any patient on active drug who experiences clinically significant optic disc edema on funduscopic examination, clinically significant functional visual change from baseline, or clinically significant RNFL thickening by SD-OCT that is deemed study drug related will undergo a lumbar puncture to rule out increased intracranial pressure and will be prohibited from receiving further doses of study medication.

In addition, if clinical signs or symptoms (such as severe headache, dizziness, lethargy, vomiting, seizures, pulsatile tinnitus) raise the suspicion of increased intracranial pressure, a lumbar puncture will be performed. Lumbar punctures should include measurement of opening pressure in the lateral decubitus position. For all patients who undergo lumbar puncture, cerebrospinal fluid will be collected for analysis of glucose, protein, red blood cells (RBCs), white blood cells (WBCs), and differential and potentially cryptococcal antigen and bacterial culture.

6.1.4.6 Cardiac hypertrophy

Increased heart weights were observed in rats with a corresponding slight to moderate increase in thickness (hypertrophy) of the left ventricular wall and interventricular septum of the heart in a 26-week study. In a 4-week study, increased heart weight without microscopic findings of hypertrophy were observed. There were no changes in heart weight or findings of cardiac hypertrophy or other abnormal microscopic changes observed in the hearts of monkeys. However, transient non-adverse increases in heart rate were observed after single doses, with no observed effects on other hemodynamic parameters, blood pressures, or ECG assessments.

6.1.4.7 Gastrointestinal Ulcerations

Gastrointestinal toxicities characterized by the presence of bloody feces or vomit and microscopic findings of gastric erosions or ulcerations were observed in the 4-week toxicity study in monkeys but generally resolved during the 4-week recovery period. GI toxicity was the cause of moribundity and early euthanasia in two animals. In the 39-week study in monkeys, no GI toxicity was observed. Potential GI toxicities will be evaluated regularly by assessing for adverse effects that may indicate intolerability, such as nausea, vomiting, or diarrhea.

6.1.4.8 Glycemic Dysregulation

In nonclinical studies, effects on glucose regulation (rat and monkey) and brown adipose tissue macrovesicular vacuolation (monkey) were consistent with GDC-0134 potentially interfering with glycemic regulation. Serum blood glucose and body temperature will be monitored.

6.1.4.9 Hepatotoxicity

Nonclinical studies with GDC-0134 showed an increase of unconjugated bilirubin (2-4x) in rats, in the absence of elevated liver enzymes. No increases of unconjugated bilirubin or liver enzymes were observed in cynomolgus monkeys. Patients with abnormal baseline clinical laboratory test results will be excluded from GDC-0134 study protocol(s), as will patients positive for anti-HCV or HBsAg.

Liver function tests, including aspartate aminotransferase (AST), alanine aminotransferase (ALT), alkaline phosphatase, and total and fractionated bilirubin, will be monitored closely. Cases of potential drug-induced liver injury that include an elevated ALT or AST in combination with either an elevated bilirubin or clinical jaundice, as defined by Hy's Law, must be reported to Sponsor as an AE of special interest (AESI) within 24 hours (see Section 8.1.3).

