2.2 OVERVIEW OF GDC-0134 CLINICAL DEVELOPMENT

There have been two recent clinical studies evaluating GDC-0134. A randomized, double-blind Phase I study (Study GN29823) is ongoing in patients with ALS to evaluate the safety, tolerability and pharmacokinetics (PK) of GDC-0134. An open-label, cross over clinical pharmacology study (Study GP39778) is completed and was conducted in healthy female subjects of non-childbearing potential to investigate the relative bioavailability of two formulations of GDC-0134 and to evaluate the effect of food, a proton pump inhibitor (PPI), and applesauce preparation on GDC-0134 absorption and disposition.

As of 22 October 2018, Study GN29823 has enrolled 43 male and female patients with ALS who have received GDC-0134 or placebo. GDC-0134 has had a favorable safety profile in all single dose, multiple-dose, and open-label safety expansion (OSE) cohorts evaluated in Study GN29823. There have been no reported deaths; one serious adverse event (SAE) in the OSE stage at 400 mg once daily (QD) (life-threatening thrombocytopenia confounded by concomitant medications including cephalexin and ibuprofen), one dose-limiting AE (DLAE) in multiple ascending dose (MAD) stage at 800 mg (non-serious AE of blurred vision with no objective findings), and four withdrawals due to AEs have been observed (two in the single ascending dose [SAD] stage [one asymptomatic non-serious increase in intraocular pressure (IOP); and one non-serious asymptomatic increase in blood bilirubin 161 days after last dose], one in the MAD [the DLAE described previously] and one in the OSE [the SAE described previously]) (see the Investigator Brochure [IB] for full details [10]).

In the completed Study GP39778, a total of 18 healthy female subjects each have received four single doses (200 mg each) of GDC-0134, separated by approximately 3 weeks. Overall, single doses of GDC-0134 were well tolerated. There were no deaths, no SAEs, and no withdrawals due to AEs. There was one severe AE of asymptomatic increased transaminases approximately 2 days after dosing with formulated GDC-0134 with high-fat meal in combination with 20 mg rabeprazole following prior administration of rabeprazole for 3 days (see the IB for full details [10]).

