In Part 1, Periods 1 and 2, eligible subjects will receive 800 mg of either GDC-0134 F16 capsules or the current clinical material, GDC-0134 F09 capsules (Ro 704-0814/F09), orally with a standard meal on Day 1 according to the randomization schedule. Subjects will be confined to the CRU from Check-in (Day -1) until Discharge on Day 3. Subjects will be required to return to the CRU for outpatient visits on Days 5, 7, and 15 (or at Early Termination [ET]). Check-in (Day -1) for Period 2 will occur 20 days after dosing in Period 1.

[figure not shown]
Part 2

In Part 2, Periods 1 and 2, subjects will receive 800 mg of GDC-0134 F15 or the current clinical material, GDC-0134 F09 capsules, after an overnight fast according to the randomization schedule on Day 1. Subjects will not receive food for 4 hours postdose. Part 2 may occur before, after, or in parallel with Part 1.

Subjects will be confined to the CRU from Check-in (Day -1) until Discharge on Day 3 during each period. Subjects will be required to return to the CRU for outpatient visits on Days 5, 7, and 15 (or at ET). Check-in (Day -1) for Period 2 will occur 20 days after dosing in Period 1.

A detailed list of assessments is included in Table 7-1 and Table 7-2.

[figure not shown]
Figure 1 Study Schematic of Crossover Design – Part 1

Standard meal

Note: F09 capsules = current clinical material of GDC-0134; F16 capsules = newly developed capsule formulation with GDC-0134 malate drug substance

Figure 2 Study Schematic of Crossover Design – Part 2

Fasted

Note: F09 capsules = current clinical material of GDC-0134; F15 capsules = newly developed capsule formulation with GDC-0134 free base

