	0.5	3 minutes	GDC-0134 (Plasma)
	1	5 minutes	GDC-0134 (Plasma)
	1.5	5 minutes	GDC-0134 (Plasma)
Day 1	2	10 minutes	GDC-0134 (Plasma)
	3	10 minutes	GDC-0134 (Plasma)
	4	10 minutes	GDC-0134 (Plasma)
	6	10 minutes	GDC-0134 (Plasma)
	8	10 minutes	GDC-0134 (Plasma)
	12	10 minutes	GDC-0134 (Plasma)
Day 2	24	10 minutes	GDC-0134 (Plasma)
Day 3	48	30 minutes	GDC-0134 (Plasma)
Day 5	96	6 hours	GDC-0134 (Plasma)
Day 7	144	6 hours	GDC-0134 (Plasma)
Day 15	336	6 hours	GDC-0134 (Plasma)
Day 22 ¹	504	6 hours	GDC-0134 (Plasma)

Table 7-3 Plasma Pharmacokinetic Sampling Scheme (All Study Periods)

NA = not applicable; PK = pharmacokinetic.

^{1.} The predose sample in the second period in each part (Period 2) will be used as the Day 22 PK sample for the first period in each part (Period 1).

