8.3.1.6 ABNORMAL LIVER FUNCTION TESTS

The finding of an elevated ALT or AST ($>3 \times ULN$) in combination with either an elevated total bilirubin ($>2 \times ULN$) or clinical jaundice in the absence of cholestasis or other causes of hyperbilirubinemia is considered to be an indicator of severe liver injury (as defined by Hy's Law). Therefore, PIs must report as an AE the occurrence of either of the following:

- Treatment-emergent ALT or AST >3 × ULN in combination with total bilirubin >2 × ULN;
- Treatment-emergent ALT or AST $>3 \times$ ULN in combination with clinical jaundice.

The most appropriate diagnosis or (if a diagnosis cannot be established) the abnormal laboratory values should be recorded on the AE eCRF (see Section 8.3.1) and reported to the Sponsor immediately (i.e., no more than 24 hours after learning of the event), either as an SAE or an AESI (see Section 8.4.2).

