APPENDIX B – APPROXIMATE MAXIMUM BLOOD VOLUME COLLECTED

	Sample Volume	Number of	Total Volume
	(mL)	Samples	(mL)
Serology	7	1	7
Clinical Laboratory Evaluations (including serum	12.5	5	62.5
pregnancy and serum FSH)	12.5	5	02.5
Coagulation	3	3	9
Tuberculosis (Quantiferon [®] TB Gold)	4	1	4
PK Samples	4	31	124
WGS Sample	6	1	6
		Total per part	212.5

Number of samples collected in each part of the study

FSH = follicle-stimulating hormone; PK = pharmacokinetic; TB = tuberculosis; WGS = whole genome sequencing.

Note: Additional samples may be drawn for safety purposes.

If subjects participate in both parts of the study, the total blood volume will be approximately double that indicated in the table (~425 mL).

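### The first scheduled liver test after dosing comes 20 days (Period 1) and 14 days (Period 2) later, so a short-lived transaminase rise could be missed before the second 800 mg dose

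*Protocol*

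**What the plan says.** Section 6.1.4.9 of the protocol names hepatotoxicity as a potential risk and commits to the following: "Liver function tests, including aspartate aminotransferase (AST), alanine aminotransferase (ALT), alkaline phosphatase, and total and fractionated bilirubin, will be monitored closely".

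Section 7.8 leaves the timing of laboratory tests to Tables 7-1 and 7-2. In both tables the chemistry row is marked at Screening and on study Days -1, 21, 36 and 43. Dosing is on Days 1 and 22. On the Period 1 interval, Section 4.1 says: "Check-in (Day -1) for Period 2 will occur 20 days after dosing in Period 1".

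Section 2.2 describes the completed healthy-volunteer study, in which 18 women each received four single 200 mg doses. One severe adverse event is reported: "asymptomatic increased transaminases approximately 2 days after dosing with formulated GDC-0134 with high-fat meal in combination with 20 mg rabeprazole".

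Three existing provisions bear on the point:
- Section 5.2 requires laboratory values at check-in to be in range, unless the investigator judges a deviation not clinically significant.
- Section 7.13 and the schedules provide a physical examination on Day 3 of each period.
- Appendix B notes: "Additional samples may be drawn for safety purposes".

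Section 3.4.2 makes change in laboratory results, both during and after administration, a safety endpoint.

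**The concern.** The only transaminase signal that the protocol reports in healthy volunteers appeared about 2 days after dosing and had no symptoms. The schedule takes no liver sample until 20 days after the first dose. A rise that peaks in the first days and settles by Day 21 would not enter the database, and the subject could be re-dosed at 800 mg with no one aware of her first reaction.

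The safety endpoint suffers as well. SAP Section 11.5.2 lists out-of-range laboratory values, and a rise that is never sampled cannot be listed. Section 8.3.1.6 defines a reportable liver event by ALT or AST above 3 x ULN with either total bilirubin above 2 x ULN or clinical jaundice. In the early window only the jaundice route could be recognised from scheduled assessments.

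**Working it through.** **1. Confirm the schedule against Appendix B.** The chemistry row has five marks: Screening, -1, 21, 36 and 43. Appendix B counts 5 clinical laboratory samples at 12.5 mL, and 5 x 12.5 = 62.5 mL, as printed. Its other rows also reproduce: PK samples 2 x 16 - 1 shared = 31, or 124 mL; total 7 + 62.5 + 9 + 4 + 124 + 6 = 212.5 mL.

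**2. Time from dose to first scheduled liver test.**
- Period 1: Day 21 - Day 1 = 20 days.
- Period 2: Day 36 - Day 22 = 14 days.

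**3. Time from the point at which the earlier case was seen.** About 2 days postdose is study Day 3 in Period 1 and Day 24 in Period 2.
- Period 1: 21 - 3 = 18 days.
- Period 2: 36 - 24 = 12 days.

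**4. Could a rise settle within that time?** The documents give no peak level and no recovery time, so this is an illustration. Assume a peak of P x ULN on Day 3 of the period and exponential decline. The value reaches 1 x ULN after d days when its half-life is d x ln 2 / ln P. Any shorter half-life means the rise is back in range at the first test.

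| Peak | Period 1 (d = 18) | Period 2 (d = 12) |
|---|---|---|
| 5 x ULN | 7.8 days | 5.2 days |
| 10 x ULN | 5.4 days | 3.6 days |
| 20 x ULN | 4.2 days | 2.8 days |

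The same model can be run the other way. The time back to ULN, in days after dosing, is 2 + log2(P) x half-life. With half-lives of 24 to 72 hours, a 3 x peak is back in range 3.6 to 6.8 days after dosing and a 20 x peak 6.3 to 15.0 days after dosing. All of these precede the Period 1 test at 20 days. At 120 hours, a 10 x peak clears at 18.6 days and is still missed, while a 20 x peak clears at 23.6 days and would be seen.

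**5. Would anything else find it?**
- The Section 5.2 check finds only a rise that persists to Day 21.
- The adverse event inquiries and the optional safety samples need a symptom or other prompt, which an asymptomatic rise does not give.
- The Day 3 examination could show jaundice but not an isolated enzyme rise.

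**6. Is there an existing draw to use?** Table 7-3 has a 48-hour PK sample on Day 3 of each period, when subjects are still in the unit. No liver test is attached to it.

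**The case against.** The strongest objection is that the precedent is weak. It is a single case, after rabeprazole and a high-fat meal, and acid-reducing drugs are barred here. Section 2.5 says that doses up to 1200 mg daily were well tolerated in patients, at more than 5-fold the exposure of a single fasted 800 mg dose. Section 6.1.1 lists no identified risks. This stands as a reason to think the risk is small. It does not dispose of the case: Section 2.3 puts exposure with a proton pump inhibitor plus a high-fat meal at 46% to 99% of control, so raised exposure does not readily explain it, and the present dose is 800/200 = 4 times larger.

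The second objection is that transience is assumed. That is correct. Section 2.2 gives the approximate time of the event, not its peak or its course. The calculation shows that a rise could be missed, not that one is likely.

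The third is that re-dosing harm within a part applies to Period 1 only. That also stands. The Period 2 test is justified by the laboratory safety endpoint, not by re-dosing.

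The fourth is that close monitoring sets no frequency and that Tables 7-1 and 7-2 govern. This is fair as a reading of the text. The point is therefore a weakness in the design rather than a formal contradiction. Even so, a first test at 20 days is hard to describe as close monitoring.

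Finally, a Day 3 sample would miss a rise that develops later and settles by Day 21. That is true; the proposal covers the window in which the earlier case was seen, not every possibility.

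**Conclusion.** The concern holds. The schedule contains no postdose liver test for 20 days in Period 1 and 14 days in Period 2, and the existing safeguards would not detect an isolated, asymptomatic enzyme rise that settles in between. The day counts follow directly from the tables and are confirmed by Appendix B. The clinical consequence is less certain: it depends on an undocumented recovery time and on the relevance of one confounded case. The liver event of special interest would be missed only if bilirubin also rose without visible jaundice, and an isolated transaminase rise would not meet that definition even if measured. The primary PK comparison is unaffected. The change should be made because it is cheap and bears on subject safety, not because a serious risk has been shown.

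**What to change.** - **Tables 7-1 and 7-2:** add ALT, AST, alkaline phosphatase, and total and direct bilirubin on Day 3 of each period (study Days 3 and 24). Draw them with the 48-hour PK sample, before breakfast and before discharge, so that the 8-hour fast in Section 7.8 is kept.
- **Section 5.2:** add a sentence requiring the investigator to review the Period 1 Day 3 liver results before Period 2 dosing. There are 22 - 3 = 19 days in which to do so.
- **Appendix B:** add a row for two samples of at most 12.5 mL each. This is an upper bound, because the 12.5 mL figure also covers pregnancy and FSH tests.

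Cost: at most 2 x 12.5 = 25 mL per part, taking the total from 212.5 to 237.5 mL, or from about 425 to about 475 mL for a subject in both parts. No new visit or procedure is needed. The change requires a protocol amendment with IRB approval (Sections 10.1 and 10.5), and some incidental abnormal values will have to be followed up.
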